**MerFISH:** In conjunction with [name] (Biomedical Sciences, Cedars-Sinai), frozen tumor samples will be submitted for copy number and spatial assessment of thousands of different RNA species in single cells using fluorescence in situ hybridization (FISH). The eventual goal of this technology is to build a 3-D model of the tumor microenvironment with data on expression levels of various RNAs in tumor, stroma, and immune infiltrate. Changes in gene expression levels through the course of therapy will allow for the identification of drivers of safety and response.

**Single-cell RNA Sequencing:** In collaboration with [name], correlative endpoints have been designed to establish the immunogenic contribution of RT to checkpoint blockade therapy

and define the molecular signatures that are associated with amplified tumor immunogenicity. Single cell gene expression profiling will be applied to research biopsies performed prior to pembrolizumab (in the TNBC cohort only) and in all cohorts, sequentially following administration of pembrolizumab and pembrolizumab + RT to identify tumors with an immunogenic response. For each biopsy, 10,000 live single cells will be isolated from the mixture using Fluorescence Activated Cell Sorting (FACS), disregarding cell type. These cells will be profiled individually using the 10X genomics single cell RNA-sequencing platform. The result of this processing will be a set of 10,000 gene expression signatures for each biopsy, where each profile informs on the type and molecular state of a single tumor cell.

**Optional MR Breast Imaging:**

Imaging will be performed as an optional sub-study after consent at baseline, within 14 days prior to C1D1, prior to C2D1 (+/- 5 days), and prior to Week 7(+/- 5 days) at the time of initiation of standard of care treatment. Timing to coincide with research biopsies.

If the patient agrees to participate in the study, he/she will undergo the following procedures:

- The patient will be set up in the prone position. A breast MR coil will be placed on the patient body.
- The patient will be asked to breathe freely. Standard breast MR sequences, including T2 weighted sequences (anatomy and analysis), T1 gradient-echo sequences will be performed and used as a comparison.
- Research MR sequence including free-breathing dynamic contrast-enhanced (DCE) MR, diffusion MR, multi-tasking 4D-MR with T1/T2 map and Chemical exchange saturation transfer (CEST) will be performed on the patient.
- The patient will be given contrast for the DCE sequence.
- The MR scan will take 1-1.5hrs. A patient arrives at the research imaging core 45min before the scan for consent and IV placement.

Data will be collected by the imaging core and analyzed by the [name] Lab in conjunction with his collaborators in the Cedars-Sinai Biomedical Imaging Research Institute (BIRI).

**Optional Fecal Samples for Microbiome Analysis:**

In conjunction with [name] (Radiation Oncology, Cedars-Sinai), optional fecal samples will undergo microbiome analysis. Kits for sample collection will be provided to all participants who opt to participate in this optional part of the trial, upon registration to the trial. Each kit will be provided with a pre-labeled box to be shipped back by the patient for analysis to the laboratory of the CSMC PI who will be conducting this analysis:

[name]  
Cedars-Sinai Medical Center  
[name]  
[name]

All specimens will contain the subject's name and date of collection. The shipping and receipt of specimens will be tracked in a database and by emails sent to [name] and the PI. Alternatively, samples may be delivered to [name] lab via the study coordinator.

## 8.2 Sample Collection / Specimen Banking

Research bloods to be used for flow cytometry analysis, measurement of circulating cytokines, and TCR sequencing will be collected prior to C1D1, on C2D1, and at the time

of initiation of standard of care treatment. Samples will be frozen and stored for subsequent analysis in the laboratory of [name].

Research biopsies will be conducted prior to C1D1 (standard of care diagnostic biopsy can be used if sufficient archived tissue available for the ER+ cohort), on C2D1, and at the time of initiation of standard of care treatment. If subsequent standard of care treatment is breast-conserving surgery, excision of tumor tissue+/- surrounding normal tissue can be collected in lieu of biopsy. At each time point, at least 2 cores (1cm each) will be collected. One will be frozen for flow cytometry analysis and MerFISH and the other will be paraffin embedded for TIL score, mIHC, and TCR and exome sequencing. For the ER+ cohort, if archived tissue is used in lieu of the first research biopsy, flow cytometry and MerFISH will not be conducted on this sample as fresh or frozen tissue is required for these studies.

If subjects receive neoadjuvant systemic therapy prior to proceeding to surgery as part of SOC treatment, fresh specimens may be collected at the time of surgery.

## **9.0 STATISTICAL CONSIDERATIONS**

### **9.1 Sample Size**

#### **Phase Ib:**

It is imperative that any experimental pre-operative therapeutic innovation not undermine the timing of curative-intent treatment in localized breast cancer, the primary endpoint for the Phase Ib study is safety/tolerability, as defined by the number of patients who do not necessitate a delay in standard of care treatment (breast surgery or neoadjuvant systemic therapy followed by breast surgery). A small number of patients of TNBC will be included in this cohort to establish safety of the regimen as described below for consideration for further study. Along with safety, assessment of TILs through the course of treatment in this cohort will establish the immunogenicity of this combination. If at least 80% of the first 10 subjects in the TNBC cohort proceed with standard of care therapy without delay, the combination will be deemed safe in the cohort, and enrollment in the HR+ cohort (10 subjects) will occur at that time.

#### **Phase II:**

Once the protocol has been determined to be safe and the protocol modified accordingly, we will employ Simon's two stage trial design. For this cohort, the null hypothesis that the true response rate is 10% will be tested against a one-sided alternative. In the first stage, 22 patients will be accrued. If there are 2 or fewer responses in these 22 patients, the study will be stopped. Otherwise, 18 additional patients will be accrued for a total of 40 patients. The null hypothesis will be rejected if 8 or more responses are observed in 40 patients. This design yields a type I error rate of 0.04 and power of 0.80 when the true response rate is 25%.

---

## 9.2 Data Sets Analyzed

### Data Analyses/Study Endpoints

#### 9.2.1 Efficacy Analysis

The primary analysis will be based on an intention-to-treat approach and will include all subjects who receive a dose of study drug.

Phase Ib:

The primary efficacy endpoint will be feasibility as defined by the number of patients who do not necessitate a delay in standard of care treatment. Let  $P_d$  be the true probability that a patient experiences a delay. The trial will stop if there is statistical evidence that  $P_d$  exceeds 20%. We will use a Bayesian sequential design by checking whether  $P_d$  exceeds this threshold value after 3, 6, 9, ... patients are evaluable for feasibility. The decision rule is to stop the trial if the posterior probability that  $P_d$  exceeds 0.20 is 0.95 or more;  $P(P_d > 0.2 | \text{data}) > 0.95$ . A non-informative prior distribution for  $P_d$  will be used. Table 9.2.1 gives the stopping rules for the design at each look and column 2 gives the maximum number of patients with delay in order for the trial to proceed. Stopping rules will also apply for any patients with clinical progression of disease during study treatment, although this is expected to be uncommon. For example, if 4 or more delays in treatment are observed after enrolling 6 patients, the trial stops. The third column gives the probability of stopping the trial when in fact, the true  $P_d = 0.20$ . This is the equivalent of the Bayesian type I error probability. The target type I error probability was set at 0.05.

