**Table 9.2.1 Stopping rules based on four interim looks**

Number of Patients	Number to Continue	Probability to Stop	Cumulative Probability to Stop
3	2	0.008	0.008
6	3	0.013	0.021
9	4	0.010	0.031
10	4	0.011	0.042

Number to continue is the maximum number of delays in standard of care treatment for not stopping the trial.

Table 9.2.2 gives the design operating characteristics under selected values of the true probability  $P_d$  for the HR+ cohort. It gives the probability of stopping the trial under the alternative hypothesis, the expected sample size, and the average sample size given that the trial stopped. For example, if the true value of  $P_d$  is 0.5, then there is an 64% chance that the trial is stopped early and the average sample size is about 8. On the other hand, there is a small chance of stopping the trial if  $P_d$  is small; 0.3% chance of stopping the trial when in fact  $P_d = 0.1$ . Tables 9.2.3 and 9.2.4 list the same operating characteristics for the TNBC cohort.

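### The Phase Ib delay rule names no prior, and under the usual symmetric non-informative priors its 0.95 cutoff does not give the boundaries or the 0.042 error rate of Table 9.2.1

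*Combined protocol and SAP*

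**What the plan says.** Section 9.2.1 (Phase Ib) defines Pd as the true probability that a patient's standard of care treatment is delayed. It stops the trial if the posterior probability that Pd "exceeds 0.20 is 0.95 or more". On the prior it says only: "A non-informative prior distribution for" Pd will be used, with no distribution or parameters there or elsewhere.

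The same paragraph says that Table 9.2.1 "gives the stopping rules for the design at each look". The table has looks at 3, 6, 9 and 10 patients and allows 2, 3, 4 and 4 delays. Its footnote reads: "Number to continue is the maximum number of delays in standard of care treatment for not stopping the trial". The worked example agrees with the table: "if 4 or more delays in treatment are observed after enrolling 6 patients, the trial stops". The cumulative stopping probability at Pd = 0.20 is given as 0.042, and "The target type I error probability was set at 0.05". For Pd = 0.5 the text reports that "there is an 64% chance that the trial is stopped early and the average sample size is about 8", which is the Table 9.2.2 entry.

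The section adds that "Tables 9.2.3 and 9.2.4 list the same operating characteristics for the TNBC cohort"; those two tables run to 20 patients. Section 3.0 restates the stopping rule without the 0.95 cutoff.

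**The concern.** The text and the table should be two descriptions of one rule. A statistician applying the text would take a usual non-informative prior for a binomial rate, compute the posterior and compare it with 0.95. A coordinator would read the count from the table. If the two give different decisions, the plan does not settle whether enrolment stops, and the stated error rate belongs to only one of them.

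The rule guards the Phase Ib primary endpoint, so the disagreement touches a decision threshold. It arises at the first look: exactly 2 delays in the first 3 patients has probability 3 × 0.2² × 0.8 = 0.096 at Pd = 0.20, and 3 × 0.5³ = 0.375 at Pd = 0.50.

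**Working it through.** **Inputs.** From Section 9.2.1: threshold 0.20, cutoff 0.95, target 0.05. From Table 9.2.1: looks at 3, 6, 9, 10 and maximum delays to continue 2, 3, 4, 4. The prior is not given, so it is an assumption here: Beta(1,1) (uniform), Beta(0.5,0.5) (Jeffreys) and Beta(0.001,0.001) (near-Haldane) cover the usual symmetric choices.

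**Step 1. The plan's own figures, from its own boundaries.** Exact sequential binomial at Pd = 0.20:

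- Look at 3: P(3 of 3) = 0.2³ = 0.008.
- Look at 6 (4 or more, having continued at 3): 0.096 × 0.104 + 0.384 × 0.008 = 0.0131. Here 0.096 and 0.384 are the probabilities of 2 and 1 delays in the first 3, and 0.104 and 0.008 those of at least 2 and of exactly 3 delays in the next 3.
- Looks at 9 and 10, by the same recursion: 0.0101 and 0.0113.
- Cumulative: 0.0080, 0.0211, 0.0311, 0.0424.

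This matches Table 9.2.1. The same boundaries give 0.003, 0.171, 0.643 and 0.844 with expected N 9.99, 9.55, 8.01 and 6.92 at Pd = 0.1, 0.3, 0.5 and 0.6, which matches Table 9.2.2. The tables are correct for the printed boundaries.

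**Step 2. Posterior at each tabled continue count.** With k delays in n and a Beta(a,b) prior, P(Pd > 0.20 | data) is the upper tail of Beta(a + k, b + n − k) at 0.20. For 2 of 3:

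- uniform: Beta(3,2), tail 1 − (4 × 0.2³ × 0.8 + 0.2⁴) = 1 − 0.0272 = 0.9728
- Haldane limit: Beta(2,1), tail 1 − 0.2² = 0.9600

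| Prior | 2 of 3 | 3 of 6 | 4 of 9 | 4 of 10 | Delays allowed at 0.95 |
|---|---|---|---|---|---|
| Beta(1,1) | 0.9728 | 0.9667 | 0.9672 | 0.9496 | 1/2/3/4 |
| Beta(0.5,0.5) | 0.9663 | 0.9562 | 0.9571 | 0.9344 | 1/2/3/4 |
| Beta(0.001,0.001) | 0.9600 | 0.9421 | 0.9437 | 0.9144 | 1/3/4/4 |
| Table 9.2.1 | continue | continue | continue | continue | 2/3/4/4 |

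At 2 of 3 every symmetric Beta(e,e) with 0 < e ≤ 1 gives 0.960 to 0.973, so the text stops and the table continues. Uniform and Jeffreys also conflict at 3 of 6, which contradicts the worked example, and at 4 of 9. Near-Haldane does not. At 10 patients text and table agree.

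**Step 3. Operating characteristics of the rule as written, N = 10.** At Pd = 0.20 the first look alone stops with probability 0.096 + 0.008 = 0.104. For 1/2/3/4 the second look adds 0.512 × 0.008 + 0.384 × 0.104 = 0.0440, the third 0.0236 and the fourth nothing, so the total is 0.1716.

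| | Table 2/3/4/4 | Text, uniform or Jeffreys | Text, near-Haldane |
|---|---|---|---|
| P(stop), Pd = 0.10 | 0.003 | 0.038 | 0.029 |
| P(stop), Pd = 0.20 | 0.042 | 0.172 | 0.120 |
| P(stop), Pd = 0.50 | 0.64 | 0.81 | 0.72 |
| Expected N, Pd = 0.50 | 8.0 | 5.6 | 6.2 |

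**Step 4. Effect with the 80% gate (TNBC Phase Ib).** The gate fails with 3 or more delays in 10: 0.3222 at Pd = 0.20. The written rule adds only the case of 2 delays in the first 3 and none in the next 7: 0.096 × 0.8⁷ = 0.0201. The total is 0.3423.

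**Step 5. Can an unstated prior reconcile text and table?** For Table 9.2.1, yes. Beta(0.2,0.8) gives 0.9316, 0.9275, 0.9344 and 0.9044 at the continue counts, and 0.9960, 0.9889, 0.9861 and 0.9757 with one more delay, so 0.95 yields exactly 2/3/4/4. Beta(0.25,0.75), Beta(1/3,2/3), Beta(0.5,1) and Beta(1,4) do the same. None of these gives Table 9.2.3 at 0.95: Beta(0.2,0.8) has 0.9513, 0.9586 and 0.9742 at 6 of 15, 7 of 18 and 8 of 20, all tabled as continue. In a grid of 349,469 Beta priors at 0.95, 38,738 gave Table 9.2.1, 440 gave Table 9.2.3 (all with prior mean below 0.07) and none gave both.

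**The case against.** The strongest reply is that nothing printed is shown to be wrong. The 0.042 is correct for its boundaries. The 0.12 to 0.17 belongs to boundaries the protocol never prints, derived from priors it never names. Many weak asymmetric priors remove the conflict with Table 9.2.1, and they need not be centred at 0.20. Table 9.2.3 is weak evidence against them, because it describes a 20-patient TNBC cohort that has been superseded, and Beta(1,4) matches it up to 18 patients and misses only at 20 (0.964 at 8 of 20). The rule is also available as counts, with a worked example, so a monitor need not compute a posterior. Finally, with the 80% gate the chance that TNBC Phase Ib fails at Pd = 0.20 moves only from 0.322 to 0.342.

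Much of this stands. The table's arithmetic is right. The worked example, the 0.05 target and Table 9.2.2 all follow the table, so it is the likely intent, and the consequence in TNBC is modest. It does not remove the defect. The protocol gives the 0.95 posterior criterion as the decision rule and the table as its result. A reader told only that the prior is non-informative would reach for uniform or Jeffreys, and either contradicts the table at three of the four looks. If an asymmetric prior was used, it has to be stated. The HR+ cohort has no stated 80% gate to soften the difference.

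**Conclusion.** The concern holds. The prior is unnamed, and under the usual symmetric non-informative priors the 0.95 cutoff and Table 9.2.1 are different rules. They part at 2 of 3 delays under every Beta(e,e) with 0 < e ≤ 1. At 3 of 6 they part only for e above about 0.26, and at 4 of 9 only for e above about 0.22. For 10 patients at Pd = 0.20 the written rule stops with probability 0.120 to 0.172, which is 2.9 to 4.1 times the stated 0.042 (0.120/0.042 and 0.172/0.042) and above the 0.05 target.

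This rests on the prior being symmetric. With Beta(0.2,0.8), for example, there is no gap in Table 9.2.1. The full error-rate gap applies to the HR+ cohort. In TNBC Phase Ib the conflict mainly changes how early enrolment stops. Because a decision threshold and its stated error rate do not match under the ordinary reading of the text, this needs correcting.

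**What to change.** Name the prior with its parameters and make cutoff, boundaries and stated error rate agree. The sponsor can choose among three routes:

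- **(a) Keep Table 9.2.1 and the 0.05 target; restate the cutoff.** For symmetric Beta(e,e) with e up to 1, the largest posterior at a tabled continue count is 0.9728 and the smallest at a tabled stop count is 0.9804, so 0.975 gives 2/3/4/4 for all of them. If Table 9.2.3 is also kept, the cutoff must lie between 0.9856 and 0.9883 (uniform) or between 0.9817 and 0.9849 (Jeffreys). Cost: the plan then shows that stopping needs more evidence than 0.95.
- **(b) Keep 0.95 with a named symmetric prior; replace the boundaries.** These become 1/2/3/4 (uniform, Jeffreys) or 1/3/4/4 (near-Haldane). Table 9.2.2, the stated error rate and, under uniform or Jeffreys, the 6-patient example change with them. Cost: the error rate rises to 0.17 or 0.12, above the target.
- **(c) For the 10-patient design only, keep 0.95 and Table 9.2.1 and state the asymmetric prior that yields it.** Cost: that prior can no longer simply be called non-informative.

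Whichever route is taken, Section 3.0 should carry the same cutoff, and one look schedule should be used throughout. At present the Schema and the Study Population text have 3/6/9, Section 3.0 has both 3/6/10 and every 3 patients, and Table 9.2.1 has 3/6/9/10. Tables 9.2.3 and 9.2.4 should be replaced or removed, since the current TNBC cohort is 10 plus 40. In Table 9.2.3 the increment at 20 patients is printed as 0.009 but recomputes to 0.0009 (0.0484 − 0.0475); its cumulative 0.048 is right.

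These are edits to the Schema, Section 3.0 and Section 9.2.1. Sample size and data collection do not change.

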**Table 9.2.1 Stopping rules based on four interim looks**

Number of Patients	Number to Continue	Probability to Stop	Cumulative Probability to Stop
3	2	0.008	0.008
6	3	0.013	0.021
9	4	0.010	0.031
10	4	0.011	0.042

Number to continue is the maximum number of delays in standard of care treatment for not stopping the trial.

Table 9.2.2 gives the design operating characteristics under selected values of the true probability  $P_d$  for the HR+ cohort. It gives the probability of stopping the trial under the alternative hypothesis, the expected sample size, and the average sample size given that the trial stopped. For example, if the true value of  $P_d$  is 0.5, then there is an 64% chance that the trial is stopped early and the average sample size is about 8. On the other hand, there is a small chance of stopping the trial if  $P_d$  is small; 0.3% chance of stopping the trial when in fact  $P_d = 0.1$ . Tables 9.2.3 and 9.2.4 list the same operating characteristics for the TNBC cohort.

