### 3.0 STUDY DESIGN

#### ***Study Design***

This is a prospective, single-institution, Phase Ib/II study of the preoperative combination of pembrolizumab (pembro) and radiation therapy (RT) in patients with operable breast cancer (TNBC). The two cohorts will consist of 50 TNBC and 10 HR+ women each. Enrollment will start with the Phase Ib TNBC safety cohort. The trial will be conducted in a Bayesian design, wherein safety as assessed by lack of delay in standard of care treatment will be assessed after 3, 6, and 10 patients have initiated standard of care treatment. If at least 80% of the first 10 subjects in the TNBC cohort proceed with standard of care therapy without delay, the combination will be deemed safe in the cohort, and enrollment in the HR+ cohort, as well as continued enrollment in the TNBC cohort (40 subjects), will occur at that time.

Each cohort will be evaluated for delay in curative-intent standard of care treatment every time 3 patients complete study therapy and undergo standard of care treatment. At each of those timepoints, if the posterior probability that a patient experiences a delay in standard of care treatment exceeds 20%, the cohort will stop enrollment. In Bayesian statistics, the posterior probability of a random event or an uncertain proposition is the conditional probability that is assigned after the relevant evidence or background is taken into account. This design will assure that a cohort does not continue enrollment if early delays in standard of care treatment are seen. Enrollment will be carried out continuously and will not be stopped in order to evaluate the posterior probability of a delay. However, the number of patients undergoing assessment for a possible delay simultaneously will not exceed four in each of the 2 cohorts.

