**Table 9.2.2 Design operating characteristics under different scenarios for the true probability of  $P_d$**

True Value of $P_d$	Probability to Stop	Expected N	Expected N given that we Stopped
0.10	0.003	9.99	6.32
0.30	0.17	9.55	7.38
0.50	0.64	8.01	6.90
0.60	0.84	6.92	6.35

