**Table 9.2.3 Stopping rules based on seven interim looks**

Number of Patients	Number to Continue	Probability to Stop	Cumulative Probability to Stop
3	2	0.008	0.008
6	3	0.013	0.021
9	4	0.010	0.031
12	5	0.007	0.038
15	6	0.005	0.044
18	7	0.004	0.047
20	8	0.009	0.048

**Table 9.2.4 Design operating characteristics under different scenarios for the true probability of  $P_d$  for TNBC cohort**

True Value of $P_d$	Probability to Stop	Expected N	Expected N given that we Stopped
0.10	0.003	19.96	6.48
0.30	0.233	17.76	10.38
0.50	0.834	11.01	9.28
0.60	0.967	8.11	7.70

The co-primary efficacy endpoint will be change in TILs. TILs will be assessed in paraffin embedded samples after the study is completed and will have no bearing on impact on continued enrollment for the trial. For each cohort, the mean percent change in TIL score before treatment and after pembrolizumab alone  $\mu_1$  will be compared to the mean change in TIL score before treatment and after pembrolizumab plus radiation  $\mu_2$  using the paired t-test or Wilcoxon sign test depending on the distribution of the data. A significance of 0.05 will be used to declare statistical significance. Let  $SD(\text{diff})$  be the standard deviation of the difference in percent change in TIL score before treatment and after pembrolizumab and before and after treatment with pembrolizumab and radiation. Data from 8 evaluable patients in the HR+ cohort achieve 80% power to detect an effect size of 1.16 using a two-sided paired t-test at the 0.05 level of significance. The effect size is defined as the difference between the two means divided by  $SD(\text{diff})$ ,  $(\mu_1 - \mu_2) / SD(\text{diff})$ . This is equivalent to an absolute difference of 20% between the mean change in TIL scores assuming an  $SD(\text{diff})$  of 17%. For the TNBC cohort, assuming 16 patients are evaluable, the effect size that is detectable with the same power and type I error is 0.75.

Comparisons of clinical characteristics among cohorts will be conducted using descriptive summary statistics using median and range. Changes in TIL score will be compared between cohorts using Fishers exact test.

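### The expected sample sizes in Tables 9.2.2 and 9.2.4 count evaluated patients, not enrolled ones, and the 64% at Pd = 0.5 includes stops made when the cohort is already full

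*Combined protocol and SAP*

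**What the plan says.** Section 9.2.1 sets the feasibility looks after 3, 6, 9 and so on "patients are evaluable for feasibility". Table 9.2.1 gives limits of 2, 3, 4 and 4 delays at 3, 6, 9 and 10 patients, with this note: "Number to continue is the maximum number of delays in standard of care treatment for not stopping the trial". The worked example treats evaluated and enrolled patients as the same: "if 4 or more delays in treatment are observed after enrolling 6 patients, the trial stops".

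Table 9.2.2 gives the operating characteristics for the HR+ cohort. Its row for Pd = 0.5 reads "0.50 0.64 8.01 6.90" (true Pd, probability to stop, expected N, expected N given stopping). The text puts it this way: "then there is an 64% chance that the trial is stopped early and the average sample size is about 8". Tables 9.2.3 ("Stopping rules based on seven interim looks") and 9.2.4 do the same for a 20-patient TNBC design.

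Section 3.0 describes how enrollment runs: "Enrollment will be carried out continuously and will not be stopped in order to evaluate the posterior probability of a delay". It adds one limit: "the number of patients undergoing assessment for a possible delay simultaneously will not exceed four in each of the 2 cohorts". The same section sets standard of care treatment for about 8 weeks after trial initiation, so each patient's outcome takes about that long to become known.

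**The concern.** The tables are the plan's numerical support for the statement in Section 3.0 that a cohort will not go on enrolling if early delays are seen. A reader will take an average sample size of about 8 out of 10 as the number of patients exposed to the regimen if it causes delays half the time. If enrollment continues while outcomes are pending, more patients than that have been enrolled when the boundary is crossed, and some may have been treated. A reader will also take a 64% chance of early stopping as the chance that some of the 10 planned patients are spared. A crossing at patient 10 spares none of them.

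**Working it through.** **Inputs.** The limits 2, 3, 4, 4 at n = 3, 6, 9, 10 come from Table 9.2.1. The limits 2, 3, 4, 5, 6, 7, 8 at n = 3, 6, 9, 12, 15, 18, 20 come from Table 9.2.3. The cap of four patients in assessment per cohort comes from Section 3.0. The documents give no accrual rate, so the number k of patients enrolled but not yet evaluated at a crossing is an assumption, taken over 0 to 4. With k = 3, the slot of the patient who completes the look is still empty. With k = 4, it has already been refilled.

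**Step 1: reproduce the plan (10 patients, Pd = 0.5).** An exact binomial recursion over the looks, stopping when delays exceed the limit, gives these crossing probabilities:

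| Look | Crossing probability |
|---|---|
| 3 | 0.1250 |
| 6 | 0.2344 |
| 9 | 0.1777 |
| 10 | 0.1055 |
| Total | 0.6426 |

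The last entry is the probability of reaching patient 10 with exactly 4 delays, 0.2109, times 0.5.

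Expected N counting evaluated patients = 3(0.1250) + 6(0.2344) + 9(0.1777) + 10(0.1055 + 0.3574) = 8.01. Given stopping it is 6.90. Both match Table 9.2.2, and so do its other three rows (Pd = 0.1: 0.003 / 9.99 / 6.32; 0.3: 0.171 / 9.55 / 7.38; 0.6: 0.844 / 6.92 / 6.35). Table 9.2.1 also reproduces, with a cumulative 0.042 at Pd = 0.20. The published expected N is therefore the value for k = 0.

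**Step 2: count enrolled patients.** The looks use evaluated patients, so the crossing probabilities do not depend on k. Only the number enrolled at a crossing changes, to min(n + k, 10). For k = 4, a crossing at 3 leaves 7 enrolled and any later crossing leaves 10, so expected enrolled N = 7(0.125) + 10(0.875) = 9.62. The chance of stopping with fewer than 10 enrolled is:
- k = 0: 0.1250 + 0.2344 + 0.1777 = 0.537
- k = 1 to 3: 0.1250 + 0.2344 = 0.359
- k = 4: 0.125

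| k | Probability of crossing | Expected enrolled N | Patients spared of 10 | Probability of stopping before 10 enrolled |
|---|---|---|---|---|
| 0 | 0.643 | 8.01 | 1.99 | 0.54 |
| 1 | 0.643 | 8.55 | 1.45 | 0.36 |
| 2 | 0.643 | 8.91 | 1.09 | 0.36 |
| 3 | 0.643 | 9.27 | 0.73 | 0.36 |
| 4 | 0.643 | 9.62 | 0.38 | 0.125 |

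**Step 3: the 20-patient design, Pd = 0.5.** The crossing probability is 0.834, of which 0.815 falls before patient 20 and 0.752 at or before patient 15. Expected N with k = 0 is 11.06. With k = 3 expected enrolled N is 13.44, and with k = 4 it is 14.20. Patients spared fall from 8.94 to 6.56 or 5.80.

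**Step 4: two table entries.**
- Table 9.2.4, Pd = 0.5, from its own columns: 0.834 × 9.28 + (1 − 0.834) × 20 = 7.74 + 3.32 = 11.06. The table prints 11.01.
- Table 9.2.3, last row: the increment is printed as 0.009, but the cumulative column moves from 0.047 to 0.048. The exact increments at Pd = 0.20 are 0.0080, 0.0131, 0.0101, 0.0073, 0.0053, 0.0039 and 0.0009, which total 0.0484. The last increment should therefore read 0.001, and the cumulative 0.048 is correct.

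**The case against.** The strongest reply is that the tables are correct for what their columns name. The probability to stop is a boundary-crossing probability on evaluable patients, and it does not change with the enrollment rule. That stands. A reader might infer that the 64% itself fails once enrollment continues, but 0.643 holds for every k. Only its description as stopping early is wrong, and that fault needs no accrual assumption.

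Second, no accrual rate is given. A pipeline of 3 or 4 needs a single institution to keep the assessment slots filled over about 8 weeks. This also stands. A reader might infer that the design protects far fewer patients than claimed, or that most stops come when the HR+ cohort is full or nearly so. The documents do not establish either. With one or two patients in the pipeline, 0.359 / 0.643 = 56% of crossings at Pd = 0.5 occur with 8 or fewer enrolled, and the excess over the stated 8.01 is about 0.5 or 0.9 patients. The upper bound is 1.6 patients. That is small in absolute terms, although the whole stated saving is only 2.

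Third, these looks are not the only protection. Sections 3.0 and 9.1 open the HR+ cohort only if at least 80% of the first 10 TNBC patients have no delay. At Pd = 0.5 that requires 2 or fewer delays in 10, with probability (1 + 10 + 45)/1024 = 0.055. If Pd is similar in both subtypes, so poor a regimen would rarely reach the HR+ cohort. Section 10.5.2 also gives the research monitor authority to stop the protocol. This lowers the practical risk but does not make the stated averages correct for enrolled patients.

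Finally, a reader might infer from the printed 0.009 that the type I error reaches 0.047 + 0.009 = 0.056, above the 0.05 target. The table's own cumulative column and the exact total of 0.0484 rule that out.

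**Conclusion.** The text to Table 9.2.2 is wrong as written. An average of about 8 is a count of evaluated patients and holds for enrolled patients only with an empty pipeline, which Section 3.0 does not require. At Pd = 0.5, expected enrollment in the 10-patient design lies between 8.01 and 9.62. The probability of stopping before the cohort is full lies between 0.54 and 0.125, against a stated 64%. In the 20-patient design expected enrollment lies between 11.06 and 14.20.

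These ranges rest on three assumptions: the printed limits, independent patients with a common Pd, and a pipeline of 0 to 4. Slow accrual puts expected enrollment near the bottom of each range. Enrolled also does not always mean treated. The type I error and crossing probabilities are not in question here. The slips in Tables 9.2.3 and 9.2.4 are minor and do not affect the conclusion.

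**What to change.** - In Tables 9.2.2 and 9.2.4, label the existing expected-N columns as evaluated patients.
- Add expected enrolled N and the probability of stopping before the cohort is full, for 0, 2 and 4 patients in the pipeline, and state the accrual the team expects.
- Reword the sentence on Pd = 0.5. It could say that the boundary is crossed with probability 0.64, that stopping comes before all 10 are enrolled with probability 0.54 if no one is in the pipeline and 0.125 if four are, and that expected enrollment is 8.0 to 9.6.
- In the worked example of Section 9.2.1, refer to evaluated rather than enrolled patients.
- Correct the last increment of Table 9.2.3 from 0.009 to 0.001, and 11.01 to 11.06 in Table 9.2.4.
- Say which cohort Tables 9.2.3 and 9.2.4 now describe. They are built for 20 TNBC patients, while Section 3.0 plans 50 (the schema splits these into 10 and 40).

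The cost is about an hour of recalculation and table wording. The stopping rule is unchanged. The one drawback is that the stated figures become less favourable. If the limits are revised for another reason, the added columns must be recomputed.
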